### **5.2.2. LY2875358**

As of 1918 March 2013 2014, cumulatively 83184 subjects have received LY2875358 in the 26 ongoing clinical trials, Studies JTBA and JTBD including 123 patients receiving LY2875358 monotherapy. No dose-limiting toxicities (DLTs) have been reported for either LY2875358 monotherapy or for combination therapy with erlotinib in these studies in the dose escalation Studies JTBA and JTBD. The most frequently reported treatment-emergent adverse events (TEAEs) possibly related to LY2875358 monotherapy in Study JTBA (N=60 patients) included across all studies within the LY2875358 clinical program include fatigue (1316.3%), nausea (9.8.3%), diarrhea (5.0%), and vomiting (5.0%) (all Grade 1-7%), and 2). In this study, 3 Grade 3 AEs were considered peripheral edema (5.7%). A total of 7 possibly related to TEAEs (>Grade 3) for LY2875358: edema, monotherapy were reported: 2 events of fatigue, and 1 event each of peripheral edema, pancreatitis. In Study JTBD (N=9 patients), the only AE that study investigators have considered possibly related to LY2875358 monotherapy in >1 patient was hypoalbuminemia (n=2; 1 Grade 1 and 1 Grade 2). In this study, 1 Grade 3 AE was considered possibly related to LY2875358: anemia, nausea, and hyponatremia. A total of 45 serious adverse events (87 SAEs) have been reported in the Lilly Safety System (LSS) database in Studies JTBA and JTBD as of 1918 March 2013 2014. Of these SAEs, 5 were considered possibly related to LY2875358 by either the investigator or the sponsor, including 1 event each of thrombocytopenia, pancreatitis, dyspnea, pyrexia, and pleural effusion in a patient with non-small cell lung cancer (NSCLC) and 2 events of peripheral edema in patients a patient with pre-existing edema.

Study JTBA has been amended and is currently enrolling patients in 5 different tumor-specific expansion cohorts for dose confirmation of LY2875358 monotherapy at 2000 mg Q2W, including cohorts for renal cancer and hepatocellular carcinoma HCC patients (approximately 15

patients each). In the renal cell cancer cohort, 3 out of 15 evaluable patients demonstrated SD as their best response, including a papillary renal cancer patient who has been on study for 12 months as of October 2013 (data on file). A ~~further~~ durable, confirmed ~~PRPRs~~ for LY2875358 monotherapy ~~has~~ been observed in a patient enrolled in the HCC cohort and for a patient in the uveal melanoma with liver metastases cohort. No data are so far available for LY2875358 monotherapy in hepatocellular carcinoma and gastric cancer patients, as the ~~respective expansion cohort for hepatocellular carcinoma in JTBA and an Asian gastric cancer patient study for LY2875358 monotherapy (Study I4C-JE-JTBE) have been opened only recently is pending analysis.~~

More information about the known and expected benefits, risks, and reasonably anticipated adverse events (AEs) for ramucirumab and LY2875358 may be found in the respective molecule IBs. Information on AEs expected to be related to the investigational products may be found in Section 7 (~~Development Core Safety Information [DCSI]~~) of the respective IBs. Information on SAEs expected in the study population independent of drug exposure and that will be assessed by the sponsor in aggregate, periodically during the course of the study, may be found in Section 6 (Effects in Humans) of the respective IBs.

### **5.3.2. Rationale for Amendment (b)**

The rationale for amendment (b) is to modify Exclusion Criterion [28] and allow patients previously treated with ramucirumab to enroll in Part B1 (Gastric or GEJ adenocarcinoma) and Part B4 (NSCLC) cohorts reflecting the approval of ramucirumab for those tumors since initiation of the study.

Minor editorial changes have been made throughout the protocol to improve clarity and practicability of the protocol, secure alignment with the intended study design, and update information available for study drugs.

## **7.2. Exclusion Criteria**

- [28] Have received previous treatment with ramucirumab or LY2875358, except for patients enrolled in Cohort B1 (Gastric or GEJ adenocarcinoma) and B4 (NSCLC) who may have received previous ramucirumab treatment.

### **9.2.3. Dose Adjustments and Delays**

In case the toxicity is specifically attributable to 1 of the 2 experimental study drugs in the opinion of the investigator (eg, ramucirumab-related hypertension), the patient may continue to receive the other study drug following the regularly scheduled Q2W treatment time points (eg, LY2875358). In this setting, treatment of the withheld study drug (eg, ramucirumab) should be resumed at the next regularly scheduled Q2W treatment time point of the continued study drug (eg, LY2875358) following the resolution of the event causing the hold. Make-up doses of the withheld study drug occurring between regularly scheduled Q2W treatment time points are not permitted in order to keep the administration of both study drugs synchronized to the same study days (ie, Day 1 or 15 of a cycle). In situations where >2 consecutive doses have been missed, events related to the missed doses have resolved, and there is evidence of ongoing disease

control, continuation of ramucirumab and/or LY2875358 may be considered and must be discussed with the Lilly clinical team.

### **9.5. Concomitant Therapy**

~~Patients should receive full supportive care, with the exception that the. The routine use of granulocyte colony stimulating factors (G-CSF) is not permitted during this study. Patients should not receive G-CSF prophylactically in any cycle. Granulocyte colony stimulating factors may only be used for patients who have absolute neutrophil count  $<0.5 \times 10^9$ , neutropenic fever, or documented infections while neutropenic. Granulocyte colony stimulating factors or pegylated G-CSF must be discontinued at least 24 hours or 1 week before the start of the next cycle of treatment, respectively. If clinically indicated, the use of G-CSF is permitted during investigational therapy at the discretion of the investigator. G-CSF or similar agents are recommended following Grade 3 or 4 neutropenia of duration  $>5$  days or following any incidence of febrile neutropenia (ANC  $<1.0 \times 10^9/L$  with temperature  $\geq 38.5^{\circ}\text{C}$ ).~~

### **12.1. General Considerations**

Up to approximately 5570 patients may be enrolled in this multicenter Phase 1b/2 study with an open-label, dose escalation design. Patients will be enrolled into cohorts sequentially without randomization to dose level. During dose escalation (Part A), the total samples size per cohort will be determined by DLTs (up to 6 patients per cohort before establishing the MTD). For the tumor-specific expansion cohorts (Part B), additional patients will be enrolled within 3 cohorts for specified tumor types (approximately 15 patients per group). The sample size of approximately 15 patients for the tumor-specific expansion cohorts was selected to allow adequate assessment of safety at the recommended dose and to identify evidence of activity worthy of further investigation in Phase 2.

Leo Document ID = bb87f68c-a79e-4eal-9ced-9d0e3d706a73

Approver: PPD

Approval Date & Time: 12-Mar-2015 16:06:58 GMT

Signature meaning: Approved

Approver: PPD

Approval Date & Time: 13-Mar-2015 10:35:44 GMT

Signature meaning: Approved

6.11.3. Deaths, Other Serious Adverse Events, and Other Notable Adverse Events	20
6.11.4. Clinical Laboratory Evaluation	20
6.11.5. Vital Signs and Other Physical Findings	21
6.11.6. Electrocardiograms	21
6.11.7. Transfusion Data	21
6.11.8. X-Ray Data	21
6.12. Efficacy Analyses	21

6.13. Bioanalytical and Pharmacokinetic/Pharmacodynamic Methods.....	23
6.13.1. PK/PD Analyses.....	23
6.13.2. Biomarker Analyses	23
6.14. Subgroup Analyses.....	24
6.15. Protocol Violations.....	24
6.16. Interim Analyses and Data Monitoring	25
6.17. Planned Exploratory Analyses.....	25
6.18. Annual Report Analyses.....	25
6.19. Clinical Trial Registry Analyses	26
7. References	28

Table of Contents

Table	Page
Table JTBF.5.1. Multiple cohorts testing characteristics: Comparisons of chance of observing at least 1 patient with a clinical response between combination of ramucirumab and LY2875358 and ramucirumab monotherapy cohorts	11
Table JTBF.5.2. Previously Observed Antitumor activities of Ramucirumab Monotherapy on Gastric or GEJ adenocarcinoma, Hepatocellular carcinoma, and Renal cell cancer	11
Table JTBF.6.1. Data Handling Conventions and Rules	13

Table of Contents

Figure		Page
Figure JTBF.5.1. Study design for I4C-MC-JTBF.....		8

3. Revision History

This is the second version and was written to include a new cohort of NSCLC in Part B and provide further statistical justification in Section 5.2 Determination of Sample Size. SAP version 2 is approved before any interim analyses in Part B are conducted.

The key changes of the second version are:

- In Section 5.2, sample size is updated due to the addition of NSCLC cohort. Weighted average power is calculated to further justify the clinical utility of the biomarker. Table JTBF 5.3 is added to show the operating characteristics of Simon's optimal two-stage design, which provides details when further patients may be added to enroll up to approximately 45 patients per cohort.
- More details about the definition of PFS are provided in Section 6.12.

4. Study Objectives

4.1. Primary Objective

The primary objective of this study is to determine a recommended schedule and dose range for LY2875358 that may be safely administered in combination with a fixed regimen of ramucirumab to patients with advanced and/or metastatic cancer.

As a co-primary objective for Part B, this study will evaluate preliminary antitumor activity observed with LY2875358 in combination with a fixed regimen of ramucirumab, in tumor specific expansion cohorts, in terms of overall response rate (ORR).

4.2. Secondary Objectives

The secondary objectives of this study are:

- To characterize the safety and toxicity profile of LY2875358 in combination with a fixed regimen of ramucirumab
- To evaluate the pharmacokinetics (PK) of ramucirumab and LY2875358 when given in combination
- To document any antitumor activity observed with LY2875358 in combination with a fixed regimen of ramucirumab
- To evaluate incidence and levels of antitherapeutic antibodies against ramucirumab and LY2875358 when given in combination.

4.3. Exploratory Objectives

The exploratory objectives of this study are:

[figure not shown]
- To evaluate tumor tissue and blood for biomarkers related to the VEGF and MET signaling pathway and tumor biology of the respective tumor types enrolled in the study, which may include but are not necessarily limited to tumor expression (eg, MET and VEGFR-2) and circulating biomarker (eg, VEGF-A, HGF, extracellular cleaved domain of MET [MET ECD]) and their potential association with the objectives of the study (including PK/pharmacodynamic [PD] biomarker relationship)
- To evaluate antitumor activity based on functional tumor imaging examinations, including but not limited to 2-deoxy-2[F-18]fluoro-D-glucose positron emission tomography (FDG-PET) or other relevant modalities.

5. Study Design

5.1. Summary of Study Design

Study JTBF is a nonrandomized, open-label, dose-escalation, multicenter Phase 1b/2 study that consists of 2 parts:

- Part A: A dose escalation part with increasing doses of LY2875358 (750-2000 mg Q2W) to determine a recommended schedule and dose range for LY2875358 that may be safely administered in combination with a fixed regimen of ramucirumab 8 mg/kg Q2W to patients with advanced and/or metastatic cancer.
- Part B: Tumor-specific expansion cohorts in patients with gastric or GEJ adenocarcinoma, hepatocellular carcinoma, renal cell cancer, or non-small cell lung cancer (approximately 15 patients each) for dose confirmation of LY2875358 in combination with a fixed regimen of ramucirumab 8 mg/kg Q2W and exploration of clinical antitumor activity (Figure JTBF.5.1).

Abbreviations: HCC = hepatocellular carcinoma; PD = pharmacodynamics; PK = pharmacokinetics; pt = patient; Q2W = every 2 weeks; Ram = ramucirumab; RCC = renal cell cancer; NSCLC= non-small cell lung cancer.

Figure JTBF.5.1. Study design for I4C-MC-JTBF.

In Part A, dose escalation of LY2875358 will follow a 3+3 dose escalation scheme to determine a recommended schedule and dose of LY2875358 in combination with a fixed regimen of ramucirumab 8 mg/kg Q2W. Patients will be enrolled in cohorts of at least 3 patients. Eligible patients will receive ramucirumab as a 60-minute IV infusion followed by LY2875358 as a 90-

minute IV infusion on Days 1 and 15 of a 28-day cycle. LY2875358 will be administered after a minimum of a 60-minute observation period (minimum of 30-minute observation period in Cycle 2 and beyond) after the end of the ramucirumab infusion on Days 1 and 15 of a 28-day cycle. If it is determined that a reduced LY2875358 infusion time is safe and feasible, the investigators will be notified in writing and the pharmacy manual updated to reflect the change.

Dose escalation of LY2875358 will be guided primarily by safety assessments during Cycle 1 (28 days); available PK and PD biomarker data may also be used as a secondary consideration. The sponsor and the investigators will review and discuss all available patient safety data prior to dose escalation. If appropriate, intermediate LY2875358 dose level (or below the LY2875358 starting dose of 750 mg) may be explored after discussion between the sponsor and the investigator. The decision will be documented in writing.

Part B is intended to confirm safety and tolerability of LY2875358 in combination with a fixed regimen of ramucirumab 8 mg/kg Q2W and to explore preliminary efficacy of the combination treatment in 3 tumor-specific expansion cohorts (approximately 15 patients each):

- Part B1: Advanced gastric or GEJ adenocarcinoma
- Part B2: Advanced hepatocellular carcinoma (excluding fibrolamellar carcinoma)
- Part B3: Advanced renal cell carcinoma (all histologies)
- Part B4: Advanced non-small cell lung cancer (squamous or non-squamous)

Part B will be opened after an interim analysis of Part A data. The dose and schedule of LY2875358 in Part B for combination with the fixed regimen of ramucirumab 8 mg/kg Q2W will be defined based upon safety, PK/PD, and antitumor activity observed in Part A. The sponsor, in collaboration with the investigators, will review Part A results prior to determining the recommended schedule and dose of LY2875358 to be studied in Part B. The decision will be documented in writing and a written notification will be sent to the Institutional Review Board (IRB) prior to enrollment of patients into Part B. No amendment will be required. If indicated by safety and/or PK/PD data, the recommended schedule and dose of LY2875358 in Part B might be individually adjusted for each tumor cohort.

To explore potential biomarkers predicting clinical activity for the combination of ramucirumab and LY2875358, availability of tumor samples after progression on the most recent line of systemic tumor therapy (or willingness to undergo a pre-study treatment tumor biopsy) will be mandatory for patients in Parts A and B. This “post-progression tumor sample” may be evaluated for biomarkers related to the VEGF and MET signaling pathway and tumor biology of the respective tumor types enrolled in the study, which may include but is not necessarily limited to MET expression/amplification and VEGFR-2. In addition, tumor tissue from any time since diagnosis of the tumor (ie, archival tumor samples) will be requested (optional) to explore any relationship between clinical activity and biomarker status based on the archival tissue versus the mandatory “post-progression tumor sample.” The analysis of both type of tumor samples is expected to critically inform any tailoring strategy for the further development of a ramucirumab and LY2875358 combination treatment.

Moreover, blood samples for exploratory biomarker analysis will be collected throughout this study which may be assessed for circulating biomarker (ie, VEGF-A, HGF, MET ECD) and their potential association with the objectives of the study.

The protocol for Study JTBF was amended prior to commencement of Part B, which may include respecification of the selected tumor types for Part B. Based on the safety and tolerability of ramucirumab in Part A, and the results of ongoing clinical and preclinical studies for ramucirumab and LY2875358 in combination with standard of care therapies, Part B4 for NSCLC was added by a protocol amendment.

The planned duration of treatment is not fixed. At the end of the first treatment cycle, each patient will be clinically evaluated for safety by the investigator before being permitted to receive the next treatment cycle. Eligible patients will receive 2 cycles of ramucirumab and LY2875358, unless 1 or more of the criteria for discontinuation (Protocol Section 8.2.1) are met. Patients who have completed 2 cycles and are receiving clinical benefit may remain on study, provided they have not met any criteria for discontinuation (Protocol Section 8.2.1).

5.2. Determination of Sample Size

To determine a recommended schedule and dose range of LY2875358 in combination with ramucirumab that may be safely administered to patients with advanced and/or metastatic cancer, an adequate patient sample size is required. A sufficient sample size will allow for an accurate evaluation of the relationship between exposure and toxicity, as well as an evaluation of the relationship between exposure and pharmacological effects using descriptive statistics and appropriate modeling techniques, if data warrant. This sample size is estimated to be a total of approximately 70 patients (6-12 [Part A] + 60 [Part B]).

For Part A, following a 3+3 dose escalation scheme, the sample size calculation assumes that cohorts will include 3 to 6 patients. If 2 cohorts for the intended 2 dose levels for LY2875358 (i.e., 750 and 2000 mg) are needed to determine a recommended dose range for LY2875358 in combination with ramucirumab, then approximately 6-12 patients will be enrolled in Part A. To ensure accurate evaluation of safety, tolerability, or PK/PD biomarkers, additional patients may be enrolled during Part A if deemed appropriate based on agreement between the investigators and the sponsor.

For Part B, the sample size of approximately 15 patients per expansion cohort was selected to allow adequate confirmation of safety and tolerability of LY2875358 in combination with ramucirumab and to identify evidence of preliminary clinical activity worthy of further investigation in Phase 2, analogous to the first stage of a Simon 2-stage design. If the true clinical RR according to RECIST for the combination of ramucirumab and LY2875358 in 1 of the tumor types selected is 10%, then there is a 79% chance of observing at least 1 patient with a clinical response, which might warrant further study of the regimen. On the other hand, if the true RR is close to the RR of ramucirumab monotherapy (for example, 3% in the REGARD trial, Table JTBF.5.2), then there is a 36.7% chance of incorrectly concluding that the regimen merits further study. Table JTBF.5.1 demonstrates chance of observing at least 1 patient with clinical response for the combination of ramucirumab and LY2875358. For instance, if the true clinical RR is 10% across all four expansion cohorts in part B, there is 49.3% probability of observing

≥ 1 responder in all four cohorts. On the other hand, if the true clinical RR is 3%, there is 74.64% probability of still observing at least 1 cohort with ≥ 1 responder. In addition, variable response to treatment due to genetic variation can be measured based on patients' post-progression tumor samples. It is assumed that 50% of the study population is expected to be biomarker positive and the true response rates are 40% and 3% in the biomarker positive and biomarker negative group respectively. Since the observed number of biomarker positive patients can vary, the sample size of 15 would give us a weighted average power of 40% (i.e. each power is weighted by its associated probability of observed number of biomarker positive patients) based on 2-sided type I error rate of 20% to detect statistically significant dependence between biomarker status and clinical response, suggesting the potential clinical utility of the biomarker for identifying the most appropriate target population.

Table JTBF.5.1. Multiple cohorts testing characteristics: Comparisons of chance of observing at least 1 patient with a clinical response between combination of ramucirumab and LY2875358 and ramucirumab monotherapy cohorts

	Response Rate	Number of cohort(s) where at least 1 patient has a clinical response				
		0	1	2	3	4
Combination	10%	0.19%	2.93%	16.51%	41.42%	38.95 %
Monotherapy	3%	16.06%	37.23%	32.38%	12.52%	1.81%

In case of significant clinical activity in any of the tumor-specific expansion cohorts, further patients may be added to enroll up to approximately 45 patients per cohort to further characterize the safety and explore clinical activity of LY2875358 in combination with a fixed regimen of ramucirumab treatment, if deemed appropriate after discussion and mutual agreement between the investigators and the sponsor. A sample size of 45 would give us a weighted average power of 83% based on 2-sided type I error rate of 5% to detect the significant dependence between biomarker status and clinical response as above. The criterion of significant clinical activity may vary based on tumor-specific response rates or landmark disease control. Table JTBF 5.2 summarizes the parameters of Simon's optimal two-stage design for each cohort. The uninteresting RR of Gastric/GEJ, HCC, RCC are referenced from previous trials JVBD, JVBPQ and JVBP (Fuchs et al. 2013). The uninteresting RR of NSCLC is based on the average RR of squamous and nonsquamous groups in the second-line docetaxel arm (Scagliotti et al. 2011). Alternatively, disease control may be considered in order to proceed with enrollment up to 45 patients per cohort if deemed appropriate. Table JTBF 5.3 summarizes landmark disease control and landmark disease control considered of interest to enroll up 45 patients per cohort. Such decisions will be documented in writing, and a written notification will be sent to the IRB prior to enrollment of further patients.

Table JTBF.5.2. Simon's Optimal Two-stage Design Parameters for Each Cohort

Tumor Type	Uninteresting RR	Favorable RR	1-sided Type I Error Rate	Power	n ₁	n	r ₁	r
Gastric/GEJ	3%	10%	0.15	0.7	14	45	1	3
HCC	10%	22%	0.1	0.75	14	42	1	7
RCC	5%	12%	0.15	0.7	13	45	1	4
NSCLC	8.5%	22%	0.1	0.8	14	41	2	6

Abbreviations: GEJ=gastroesophageal junction; HCC=hepatocellular carcinoma; n₁=number of patients enrolled in the first stage; n=total number of patients enrolled; NSCLC=non-small cell lung cancer; r₁=number of responses required to proceed to the second stage; r=total number of responses required for further investigation of the drug; RCC=renal cell carcinoma; RR=response rate.

Table JTBF.5.3. Previously Observed Antitumor activities of Ramucirumab Monotherapy on Gastric or GEJ adenocarcinoma, Hepatocellular carcinoma, and Renal cell cancer

Tumor Type	Study	n	mPFS	mOS	ORR	DCR	Landmark	Secondary CSF
Gastric/GEJ	JVBD	355	2.1mos	5.2 mos	3%	49%	12-wks PFS 40%	60%
HCC	JVBQ	42	4 mos	12 mos	10%	N/A	4-mos PFS 50%	75%
RCC	JVBP	39	7.1mos	24.8mos	5% (12 week)	64%	7.1-mos PFS 50%	75%
NSCLC	Scagliotti et al.	288	3 mos	7.7 mos	8.6%	N/A	3-mos PFS 50%	75%

Abbreviations: n: number of patients; mPFS: progression free survival in months; mOS: overall survival in months; ORR: overall response rate; DCR: disease control rate; CSF: critical success factor;

In summary, up to approximately 70 patients may be enrolled in this multicenter Phase 1b/2 study with an open-label, dose escalation design. Patients will be enrolled into cohorts sequentially without randomization to dose level. During dose escalation (Part A), the total samples size per cohort will be determined by DLTs (up to 6 patients per cohort before establishing the MTD). For the tumor-specific expansion cohorts (Part B), additional patients will be enrolled within 4 cohorts for specified tumor types (approximately 15 patients per group). The sample size of approximately 15 patients for the tumor-specific expansion cohorts was

selected to allow adequate assessment of safety at the recommended dose and to identify evidence of activity worthy of further investigation in Phase 2.

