For Part B, the sample size of approximately 15 patients per expansion cohort was selected to allow adequate confirmation of safety and tolerability of LY2875358 in combination with ramucirumab and to identify evidence of preliminary clinical activity worthy of further investigation in Phase 2, analogous to the first stage of a Simon's two-stage design. If the true clinical RR according to RECIST for the combination of ramucirumab and LY2875358 in 1 of the tumor types selected is 10%, then there is a 79% chance of observing at least 1 patient with a clinical response, which might warrant further study of the regimen. On the other hand, if the true RR is close to the RR of ramucirumab monotherapy (for example, 3% in REGARD), then there is a 36.7% chance of incorrectly concluding that the regimen merits further study. In addition, variable response to treatment due to genetic variation can be measured based on patients' post-progression tumor samples. It is assumed that 50% of the study population is expected to be biomarker positive, and the true response rates are 40% and 3% in the biomarker positive and biomarker negative group respectively. Since the observed number of biomarker positive patients can vary, the sample size of 15 would give us a weighted average power of 40% (i.e. each power is weighted by its associated probability of observed number of biomarker positive patients) based on 2-sided type 1 error rate of 20% to detect statistically significant dependence between biomarker status and clinical response, suggesting the potential clinical utility of the biomarker for identifying the most appropriate target population.

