**Table JTBF.1. Simon's Optimal Two-stage Design Parameters for Each Cohort**

Tumor Type	Uninteresting RR	Favorable RR	1-sided type 1 error rate	Power	$n_1$	n	$r_1$	r
Gastric/GEJ	3%	10%	0.15	0.7	14	45	1	3
HCC	10%	22%	0.1	0.75	14	42	2	7
RCC	5%	12%	0.15	0.7	13	45	1	4
NSCLC	8.5%	22%	0.1	0.8	14	41	2	6

Abbreviations: GEJ = gastroesophageal junction; HCC = hepatocellular carcinoma;  $n_1$  = number of patients enrolled in the first stage; n = total number of patients enrolled; NSCLC = non-small cell lung cancer;  $r_1$  = number of responses required to proceed to the second stage; r = total number of responses required for further investigation of the drug; RCC = renal cell carcinoma; RR = response rate.

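### SAP Table JTBF.5.1 uses the gastric response rate of 3% as the monotherapy rate in all four Part B cohorts, so its false-signal figures do not fit the other three

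*SAP*

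**What the plan says.** SAP 5.2 explains that "the sample size of approximately 15 patients per expansion cohort was selected" to confirm safety and tolerability and to look for preliminary activity. It gives a "79% chance of observing at least 1 patient with a clinical response, which might warrant further study of the regimen" when the true response rate is 10%. For the opposite case it writes "if the true RR is close to the RR of ramucirumab monotherapy (for example, 3% in the REGARD trial, Table JTBF.5.2" and puts the chance of a wrong conclusion at 36.7%. Protocol 8.1.1 has the same sentence: "for example, 3% in REGARD), then there is a 36.7% chance of incorrectly concluding that the regimen merits further study".

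Table JTBF.5.1 extends this to several cohorts and is titled "Comparisons of chance of observing at least 1 patient with a clinical response between combination of ramucirumab and LY2875358 and ramucirumab monotherapy cohorts". It has two rows, Combination at 10% and Monotherapy at 3%, each giving the probability that 0 to 4 cohorts show a responder. The monotherapy row reads 16.06/37.23/32.38/12.52/1.81%. The text above it gives 49.3% for a responder in all four cohorts at 10%, and 74.64% for at least one such cohort at 3%.

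The section then sets separate null rates in Table JTBF.5.2: 3% gastric/GEJ, 10% HCC, 5% RCC and 8.5% NSCLC. "The uninteresting RR of Gastric/GEJ, HCC, RCC are referenced from previous trials" of ramucirumab; the NSCLC rate comes from a second-line docetaxel arm. Both documents define r1 as the "number of responses required to proceed to the second stage". For HCC, r1 is 2 in protocol Table JTBF.1 and 1 in SAP Table JTBF.5.2.

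**The concern.** A reader of Table JTBF.5.1 would take its second row as what happens across Part B if LY2875358 adds nothing to ramucirumab. By the SAP's own null rates that is true only of gastric cancer. The other three nulls are higher, so a single responder among 15 patients is much easier to see without any added effect.

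HCC is the clearest case. Its uninteresting rate, 10%, is the rate in the Combination row, so one probability serves as the chance of success in the illustration and as the chance of a false signal in that cohort.

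This matters because ORR is co-primary for Part B, a promising cohort may grow from about 15 to about 45 patients by agreement between sponsor and investigators, and SAP 6.5 plans no multiplicity adjustment. Table JTBF.5.1 and the two percentages above it are the only multi-cohort operating characteristics in the plan. The people making those decisions should be able to read the right false-signal risk for each cohort.

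**Working it through.** **Inputs.** 15 patients per cohort and four cohorts (SAP 5.2: "additional patients will be enrolled within 4 cohorts for specified tumor types (approximately 15 patients per group"). Signal: at least 1 responder. Null rates 3%, 10%, 5%, 8.5% (SAP Table JTBF.5.2). First-stage sizes n1 = 14, 14, 13, 14 and thresholds r1 = 1, 2, 1, 2 (protocol Table JTBF.1), or 1, 1, 1, 2 (SAP). Cohorts are taken as independent.

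**Step 1: reproduce the plan's figures.** P(at least 1 of 15) = 1 − (1 − p)^15.
- p = 3%: 1 − 0.97^15 = 36.7%, as stated.
- p = 10%: 1 − 0.90^15 = 79.4%, stated as 79%.
- Monotherapy row: a binomial with four cohorts and 0.367 gives 0.633^4 = 16.06% for none and 0.367^4 = 1.81% for all four, as tabled. At least one cohort is 100 − 16.06 = 83.94%.
- Combination row: 0.79^4 = 38.95% for all four, as tabled.
- Text figures: 0.79^3 = 49.3% and 1 − 0.633^3 = 74.64%. These are three-cohort values. The table's four-cohort counterparts are 38.95% and 83.94%.

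**Step 2: each cohort at its own null, same one-responder rule.**
- Gastric: 1 − 0.97^15 = 36.7%
- HCC: 1 − 0.90^15 = 79.4%
- RCC: 1 − 0.95^15 = 53.7%
- NSCLC: 1 − 0.915^15 = 73.6%

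P(no cohort signals) = 0.6333 × 0.2059 × 0.4633 × 0.2638 = 1.6%. Combining the four cohorts gives the full distribution:

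| Cohorts with a signal | 0 | 1 | 2 | 3 | 4 |
|---|---|---|---|---|---|
| SAP table, 3% everywhere | 16.1% | 37.2% | 32.4% | 12.5% | 1.8% |
| Cohort-specific nulls | 1.6% | 13.4% | 36.6% | 36.9% | 11.5% |

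At least one: 98.4% against 83.9%. Three or more: 48.4% against 14.3%.

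**Step 3: drop NSCLC**, whose null is not a ramucirumab rate. For the other three cohorts, at least one false signal is 1 − 0.6333 × 0.2059 × 0.4633 = 94.0%, against 74.6% at a common 3%.

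**Step 4: use the Simon first stage instead**, P(at least r1 of n1) at each null.

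| Rule | Gastric | HCC | RCC | NSCLC | At least one | Three or more |
|---|---|---|---|---|---|---|
| Protocol r1 | 34.7% | 41.5% | 48.7% | 33.7% | 87.0% | 17.3% |
| SAP r1 (HCC 1) | 34.7% | 77.1% | 48.7% | 33.7% | 94.9% | 27.2% |
| SAP Table JTBF.5.1 | 36.7% | 36.7% | 36.7% | 36.7% | 83.9% | 14.3% |

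Under the protocol's thresholds the distribution for 0 to 4 cohorts is 13.0/35.1/34.7/14.9/2.4%.

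Reading r1 and r as minimum counts, the protocol's values give overall type I error 0.110, 0.098, 0.149, 0.097 and power 0.701, 0.761, 0.701, 0.806. These meet the tabled limits in every cohort. With r1 = 1 for HCC, type I error is 0.117 against the stated 0.10.

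**The case against.** The table is computed correctly for the condition it states, apart from rounding. Both documents introduce 3% as an example, and the 10% case as a hypothetical for one tumor type. At least 1 responder only might warrant further study. Expansion is to follow tumor-specific response rates or landmark disease control, after discussion, and the cohort-specific nulls, error rates and thresholds are already tabled. The analyses are descriptive, and 15 per cohort also rests on safety confirmation and biomarker power.

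Most of this stands. A reader might infer that the plan's expansion decisions carry the much higher false-go risk of Step 2. The documents do not support that: under the protocol's r1 and n1 the multi-cohort distribution is close to the table as printed. A reader might also infer that every null in Step 2 means ramucirumab with an inactive partner. For NSCLC it does not, and the documents give no ramucirumab monotherapy response rate there. The HCC rate comes from patients without prior systemic therapy (protocol 5.2.1.2), whereas this trial enrolls after standard therapy has failed or is unsuitable.

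The objection does not rescue the label. The sentence calls 3% an example; the table calls it monotherapy across four cohorts. Nor does it explain 49.3% and 74.64%.

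**Conclusion.** The point holds as a fault of input and labelling. Under the one-responder signal that the SAP uses to illustrate 15 patients per cohort, 36.7% describes gastric cancer only. The HCC, RCC and NSCLC figures are 79.4%, 53.7% and 73.6%, and the monotherapy row gives too low a chance of false signals in several cohorts. Under the protocol's Simon first stage the multi-cohort shift is small (87.0% against 83.9% for at least one cohort); with the SAP's HCC threshold it is larger (94.9%).

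Separately, 49.3% and 74.64% are wrong for four cohorts.

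These results assume independent cohorts, exactly 15 patients (or n1), the SAP's uninteresting rates as the truth, and r1 as a minimum count. This should be fixed, but it does not undermine the design.

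**What to change.** In SAP 5.2:
- Rebuild Table JTBF.5.1 with each cohort's own uninteresting and favorable rates, and state whether the rule is at least 1 of 15 or r1 of n1.
- Label 36.7% as gastric only and give 79.4% (HCC), 53.7% (RCC) and 73.6% (NSCLC) beside it.
- Note that the NSCLC null is a docetaxel-arm rate.
- Replace 49.3% and 74.64% with four-cohort values (38.95% and 83.94% on the present table's inputs), or with values from the rebuilt table.
- Reconcile HCC r1 with protocol Table JTBF.1. The protocol's 2 is the value consistent with the stated 0.10 error rate.

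In protocol 8.1.1, change only the per-cohort sentence; there is no multi-cohort table to correct.

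The cost is one recalculated table and a few sentences, with figures less favorable than those now printed. Sample size and design are unchanged.
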